2. OBJECTIVE

The primary objective is to evaluate physicians' adherence to fondaparinux prescribing information for the treatment of patients with SVT of the lower limbs without concomitant DVT.

The primary endpoint of the study is the proportion of patients with isolated SVT of the lower limbs treated with fondaparinux, for whom the prescribing information was followed (i.e., an ultrasound, or other diagnostic imaging procedure, was performed in order to rule out concomitant DVT prior to patients commencing fondaparinux therapy and the correct dose of fondaparinux [either 2.5 or 1.5mg] was prescribed).

Based on the availability of data, as identified in the feasibility phase of this study, a sensitivity analysis of the primary endpoint will be conducted, incorporating the length of the thrombus (>5 cm) and/or its distance from the sapheno-femoral junction (>3 cm).

Secondary endpoints of the study include:

- The proportion of patients with SVT of the lower limbs treated with fondaparinux, for whom an ultrasound, or other diagnostic imaging procedure, was performed in order to rule out concomitant DVT prior to patients commencing fondaparinux therapy
- The proportion of patients with SVT of the lower limbs treated with fondaparinux, for whom either 2.5mg or 1.5mg fondaparinux was prescribed.

Pending the availability of the data as identified from the feasibility study, the following will also be included as secondary endpoints of the study:

 The proportion of patients with SVT of the lower limbs treated with fondaparinux, for whom the length of thrombus was measured (<5 cm being non-adherence) The proportion of patients with SVT of the lower limbs treated with fondaparinux, for whom the distance from the sapheno-femoral junction was recorded (<3 cm being non-adherence).

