4.2. Feasibility Study

A feasibility study will be conducted in those randomly selected eligible sites to determine the availability of select data components within the medical chart. The feasibility study will comprise a simple questionnaire which will contain the variables of interest as a check list. Physicians who could act as the lead investigator at each eligible site will be asked to review the medical charts of those SVT patients meeting the criteria for the study, to determine the variables/data of interest that are routinely available for each patient. The patient charts to be reviewed will be representative of those treated by each physician within each site. Additionally, the number of patient charts to be reviewed will be equivalent to the number of eligible patients a site may have available for the main study (within the upper limits set out in the main study protocol).

The variables of interest will include as follows:

- Age
- Gender
- Renal status
- Presence/absence of concomitant DVT
- Length of thrombus
- Distance from sapheno-femoral junction
- Diagnostic procedures performed (e.g. ultrasound or other objective tests)
- Prescribed fondaparinux dose and duration.

This questionnaire will not contain any indication with regards to the overall objective of the study.

Between 12 and 18 eligible sites, proportionate to the country's population and representative of the country's main geographical regions, successfully completing the feasibility study will be invited to progress to the main study.

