5.2.1. Primary Analyses

Adherence estimates with confidence intervals will be derived using generalised estimating equations (GEE) overall and for each country [8]. The GEE will explicitly take into account the nesting of patients, per physician, within a medical practice.

Adherence in the current study will be defined as performing CUS, or other diagnostic imaging procedure, in order to rule out concomitant DVT prior to patients commencing fondaparinux therapy and ensuring that the recommended dose of fondaparinux is prescribed.

A sensitivity analysis will be conducted incorporating the length of the thrombus and the distance of the thrombus from the sapheno-femoral junction into the primary endpoint if the data is available.

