9. APPENDICES

9.1 Fondaparinux prescribing information

PRESCRIBING INFORMATION FOR USE IN PATIENTS WITH SVT

Treatment of superficial-vein thrombosis

The recommended dose of fondaparinux is 2.5 mg once daily, administered by subcutaneous injection. Patients eligible for fondaparinux 2.5 mg treatment should have acute, symptomatic, isolated, spontaneous superficial-vein thrombosis of the lower limbs, at least 5 cm long and documented by ultrasonographic investigation or other objective methods. Treatment should be initiated as soon as possible following diagnosis and after exclusion of concomitant DVT or superficial-vein thrombosis within 3 cm from the saphenofemoral junction. Treatment should be continued for a minimum of 30 days and up to a maximum of 45 days in patients at high risk of thromboembolic complications. Patients could be recommended to self-inject the product when they are judged willing and able to do so. Physicians should provide clear instructions for self-injection.

Special populations

Renal impairment

Treatment of superficial-vein thrombosis - Fondaparinux should not be used in patients with creatinine clearance <20 ml/min. The dose should be reduced to 1.5 mg once daily in patients with creatinine clearance in the range of 20 to 50 ml/min. No dosage reduction is required for patients with mild renal impairment (creatinine clearance >50 ml/min). The safety and efficacy of 1.5 mg has not been studied.

Hepatic impairment

 Treatment of superficial-vein thrombosis - The safety and efficacy of fondaparinux in patients with severe hepatic impairment has not been studied, therefore fondaparinux is not recommended for use in these patients.

Low body weight

 Treatment of superficial-vein thrombosis - The safety and efficacy of fondaparinux in patients with body weight less than 50 kg has not been studied, therefore fondaparinux is not recommended for use in these patients.

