9.3 Case Report Form

·			OFFICE U	SE ONLY
Superficial Vein Thrombosis (SVT): Case	Record Fo	rm	Doctor Number	Patient Number
Today's date:			 (dd/mm/y	ууу)
Date patient first presented with symptoms:			(dd/mm/y	
Date patient mot precented with symptome.		_ /	(aa/111111/y	,,,,,
Date patient diagnosed:	/	_/	(dd/mm/y	ууу)
Fondaparinux prescribing				
Date fondaparinux first prescribed:	/	_/	(dd/mm/y	yyy)
Fondaparinux dose initially prescribed:	mg			
Planned duration of fondaparinux treatment:	da	ays 🗌 w	veeks (please ✓ if	days or weeks)
Diagnosis				
Was SVT confirmed through imaging?	☐ Yes ☐ N	lo		
If yes, what diagnostic imaging, was performed on	this patient?			
☐ Ultrasound ☐ Venography ☐ C	T Scan	☐ MF	RI	
Other (specify:)			
If 'No', please state how SVT was confirmed:				
If imaging was not performed, please state why:				
Please state location of the SVT:	☐ Left lower	limb □R	ight lower limb	
Please state position of the SVT:	 ☐ Great saph		Lesser saph	enous
·	☐ Tributary		r (
Diagon state length of the CVT			om 🗆 Not	rocarded
Please state length of the SVT:			_	recorded
Please state diameter of the SVT:			_	recorded
Please state distance from sapheno-femoral junctic	Of 1	_ · (cm Not	recorded
Was DVT diagnosed?	☐ Yes ☐ N	lo [Imaging not p	erformed
Was symptomatic PE diagnosed?	☐ Yes ☐ N	lo		

[figure not shown]
OFFICE USE ONLY							
Doctor Number	Patient Number						

Superficial Vein Thrombosis (SVT): Case Record Form

Patient demographics						
Age:	years					
Weight:	Kg					
Gender	☐ Female ☐ Male					
Patient history						
Is there documented evidence that this patient has	renal impairment?:					
	☐ Yes ☐ No ☐ Do not know					
If Yes, Mild Moderate Severe Do	not know					
Serum Creatinine result:	µm/L					
	☐ Not assessed					
Date last calculated	/					
Creatinine Clearance result:	ml/min					
	☐ Not assessed					
Date last calculated	/					
Has this patient been previously treated for DVT, PE and/or SVT?						
	□DVT □PE □SVT					

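### The secondary endpoints on whether thrombus length and junction distance were recorded depend on a feasibility check of the same quantity, so they could be dropped where recording is poor

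*Supplement*

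**What the plan says.** Section 2 has two unconditional secondary endpoints (imaging, and dose). It then adds two more, introduced by "Pending the availability of the data as identified from the feasibility study, the following will also be included as secondary endpoints of the study". These are the proportions of patients "for whom the length of thrombus was measured (<5 cm being non-adherence" and "for whom the distance from the sapheno-femoral junction was recorded (<3 cm being non-adherence". Each therefore joins a recording criterion to a cut-off on the value.

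Other places bear on this:

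- **Section 4.2.** Feasibility is done "to determine the availability of select data components within the medical chart"; thrombus length and junction distance are on its list. Main-study sites come from those that complete it. The form (Appendix 9.2) is a tick per chart, for up to 14 charts, where the item was found.
- **Section 4.3.** The length and distance outcomes are described by value (how many patients lie beyond the cut-offs), when available.
- **Section 5.2.1.** The sensitivity analysis brings length and distance "into the primary endpoint if the data is available".
- **Section 5.2.2.** All four secondary endpoints are to be analysed, overall and per country, with no condition stated.
- **Appendix 9.1 (prescribing information).** The thrombosis should be "at least 5 cm long and documented by ultrasonographic investigation or other objective methods", with thrombosis within 3 cm of the junction excluded.
- **Appendix 9.3 (CRF).** The form asks "Please state length of the SVT" and has a matching item for distance. Each has a box for a value that is not recorded.

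**The concern.** An availability check is sensible when a missing value prevents a calculation. An endpoint on whether a value was recorded is different, because a missing value is then a result. If physicians seldom chart thrombus length, a low recording proportion is the finding. Under section 2 that same fact could be the reason for not reporting it. Where charting is good, the endpoint stays and reads well.

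The documents do not say how much availability is enough, or whether the decision is taken by site, by country or for the whole study. The choice is thus open after the relevant data have been seen. At stake is whether the study says anything about two eligibility items in the prescribing information that the imaging-and-dose endpoint does not cover.

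**Working it through.** The plan states no figure on this point, so there is none to reproduce. The check compares the sections and adds two illustrations.

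**1. Is the condition the same quantity as the endpoint?** The feasibility form yields charts with length present divided by charts reviewed. The section 2 endpoint, read as a recording measure, is patients with length measured divided by patients enrolled; a retrospective review can see a measurement only if it was charted. The numerator criterion is the same and the sites are linked. The same holds for distance.

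**2. Is the condition needed?** For the recording proportion, no. With *n* enrolled patients and *r* ticks in the not-recorded box, the proportion is (*n* − *r*)/*n*, which can be computed at any level of charting. For the proportion beyond 5 cm or 3 cm, values are needed, and a check that enough exist is reasonable.

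**3. Do the sections agree?** No. Section 2 is conditional and mixes recording with value; 4.3 is conditional and uses value only; 5.2.1 is conditional for the sensitivity analysis; 5.2.2 is unconditional.

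**4. Illustration of size.** Inputs: two-part adherence 0.80 (planning value, section 5.1) and length recorded in 0.40 (assumed). Adherence that also requires a recorded length:

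- independence: 0.40 × 0.80 = 0.32;
- upper bound: min(0.40, 0.80) = 0.40;
- lower bound with no assumption on dependence: 0.40 + 0.80 − 1 = 0.20.

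A measured length normally comes from imaging, itself part of the 0.80, so independence is doubtful. If length is recorded only in imaged patients and is unrelated to dose, the result is 0.40 × P(recommended dose). That probability is at least 0.80, which gives 0.32 to 0.40.

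**5. Illustration of selection.** Everything here is assumed: a country-level decision, 15 sites × 14 charts, intra-site correlation 0.2, between-country SD of true recording 0.15, and the same sites in feasibility and main study. There were 4,000 simulated countries per row.

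| Mean true recording | Kept if feasibility at least | Share kept | Mean main-study rate, kept | Mean main-study rate, dropped |
|---|---|---|---|---|
| 50% | 50% | 0.51 | 63% | 37% |
| 50% | 70% | 0.13 | 76% | 46% |
| 50% | 80% | 0.03 | 83% | 49% |
| 60% | 50% | 0.74 | 68% | 40% |
| 60% | 70% | 0.30 | 78% | 52% |
| 60% | 80% | 0.11 | 85% | 57% |
| 70% | 50% | 0.89 | 74% | 42% |
| 70% | 70% | 0.55 | 81% | 56% |
| 70% | 80% | 0.31 | 87% | 62% |

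The reported rate exceeds the true mean in every row. The size of the gap depends on the assumptions; its direction was the same throughout.

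**The case against.** The best defence is that these are really value endpoints. Section 2 attaches cut-offs, section 4.3 speaks only of values, and checking that values exist is ordinary feasibility work. This stands for the value part, but not for the recording part, which section 2 names expressly.

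Section 5.2.2, read alone, already commits to all four endpoints. That is true, but it does not cancel the condition in section 2, and sections 4.3 and 5.2.1 repeat an availability condition. A threshold might also sit in a separate analysis plan that is not shown. It would remove the discretion, but any threshold would still select on the outcome.

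The prescribing information does not ask for a number in the chart. An uncharted length does not prove off-label use, and a sapheno-femoral distance may not be charted for lesser saphenous, tributary or other positions, which the CRF allows. This stands and limits how unrecorded values may be scored.

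The stakes are also limited. Section 1.2 spells out the EU commitment as recommended dose and imaging to rule out DVT. The primary endpoint and two unconditional secondary endpoints cover both.

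**Conclusion.** The point holds in a limited form. In section 2, inclusion of the two recording endpoints depends on the quantity that they estimate, with no stated criterion, so they could be lost where recording is poor. Sections 2, 4.3, 5.2.1 and 5.2.2 also differ on definition and conditionality.

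A reader might infer more: that the endpoints will be reported only where recording is good, that the overall figure will cover only well-documenting countries, or that unfavourable components are being removed. The documents do not support this. They state no drop threshold and no country-level rule. After feasibility in three countries the amendment in Appendix 9.5 describes added renal detail only, and the CRF still asks length and distance of every patient. Nothing shows that these items would be the least favourable.

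The true size cannot be derived. The 40% ceiling rests on an assumed recording rate, the 32% also on independence, and the simulation on assumed thresholds and spread. The primary endpoint, sample size and power are not affected.

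**What to change.** - In section 2, remove the availability condition for the recording proportions. Report them for all enrolled patients, overall and per country, from the CRF's not-recorded boxes. Label them as recording rates, and show distance also by SVT position.
- Reconcile sections 2, 4.3, 5.2.1 and 5.2.2 so that the length and distance cut-offs form separate, value-based endpoints among patients with recorded values. Give the number with a value beside each.
- Run the sensitivity analysis of the primary endpoint on recorded values. Add a version that scores unrecorded values as non-adherent, presented as a lower bound only.

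The cost is protocol wording and a few more tables. No new data are needed, since the CRF already collects both items. The downside for the sponsor is that a low recording rate may have to be reported.

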3. STUDY POPULATION

3.1. Selection of Sites

A geographically representative sample of sites in each country will be targeted for recruitment; sites responsible for managing relatively few patients (<2 patients per month) will be excluded. Reasons for non-eligibility will be documented.

Each recruited site will have one or more physicians who routinely manage SVT patients and who make decisions regarding prescribed treatment for those patients.

3.2. Sampling Strategy for Site Recruitment

The aim of the sampling strategy will be to recruit sites and site investigators that reflect routine treatment practice in their respective countries.

A master list of potential sites will be prepared for each country, based on practice information known to ARW and its local fieldwork partners, and with additional input as required from GSK local operating companies. Sites will be stratified by geographic region and, in addition, according to resident population densities within those regions.

Sites will be sampled such that good geographical representation is achieved within each country and that the number of site investigators recruited is proportionate to the treated patient population served in each geographical region. Thus, a region with twice the estimated patient population of another will be anticipated to provide a greater number of sites and/or site investigators.

3.3. Patient inclusion and exclusion criteria

3.3.1. Inclusion Criteria

- (1) Diagnosis of SVT
- (2) Prescribed fondaparinux for the treatment of SVT
- (3) Age 18 years or older.

3.3.2. Exclusion Criteria

(1) Patients should not have been involved in any clinical trial that could influence SVT treatment during the observational period (i.e. the retrospective period during which data is recorded).

4. STUDY DESIGN

The study is a non-interventional, retrospective chart review of patients prescribed fondaparinux to treat their SVT. The study will be conducted in several EU countries. Qualified medical record abstractors will be identified at each site and specifically trained on the data collection required for the study.

It is essential that the study design and objective does not influence physician practice for treating those patients being included in the study. Consequently, the study will not begin recruitment until at least six months following availability and reimbursement of the product at the particular site. This delay should be sufficient to allow fondaparinux to be adopted into routine practice at each recruited site and to be prescribed to a sufficient number of patients per physician. Sites may be identified during this time period, however, recruitment will only begin after the six months have passed and a sufficient number of patients have accrued.

The site abstractor(s) will complete a short paper-based case report form (CRF) on the first consecutive 'n' SVT patients prescribed with fondaparinux by each physician practising at the site starting one month after the availability and reimbursement of fondaparinux, and who meet the other study inclusion criteria It is assumed that each site will have more than one physician who can provide patients for inclusion in the study. Thus, it is envisaged that one

physician will take the role of the site lead investigator, who would be the main point of contact during the study and would be responsible for coordinating site activities (e.g. assisting with EC submissions, data collection, etc.).

The lead investigator of each site will be fully briefed on the study objectives, methodology and data requirements prior to data collection.

Sites will track abstracted records by an identification log kept at the site to ensure that records can be re-accessed in the case of an outstanding query or audit. This information will not be entered into the database or retained by the sponsor. Consecutive records which fulfil the inclusion criteria are desired; however, if it is not possible to identify the date and dose of fondaparinux prescribed to eligible SVT patients in the source records, then these patient(s) may be excluded from the study.

The exclusion of any consecutive records will also be tracked.

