4.1. Site Identification

A simple survey containing a series of queries will be completed by those sites identified on the master list for each country to determine their eligibility to participate in the study.

The queries within the survey will include the following:

- Site details (such as overall number of patients)
- Number of DVT/SVT patients treated at each site
- Types and number of physicians/specialists who are managing such patients
- Diagnostic criteria employed (such as physical assessment; imaging techniques, other blood tests)
- Diagnostic tools/capabilities within each site.

The survey will not contain any indications of overall objective of the study.

Eligible sites will be stratified by geographical region and between 18 and 36 sites that are representative of each country's population distribution will be

randomly selected and invited to complete a feasibility study as a pre-cursor to being finally selected for recruitment into the study.

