9.1 Site Assessment Survey

SVT - Physician Prescribing Study Site assessment survey

Good morning/afternoon, I am calling from, a market research organisation specialising in healthcare.						
treat grate	ment of patients with Superfici	it centres for a study relating to the al Vein Thrombosis (SVT) and I would be questions to establish whether your in the study.				
Woul	d you be willing to answer these	e preliminary questions?				
☐ Ye	es 🔲 No					
If 'No	o', thank and close - record as a	'refused contact'.				
	, thank and close record as a	refused contact.				
1a.	Where do you mainly	☐ Hospital				
iu.	practice?	□ Office				
		☐ GP clinic/surgery				
		□ Other ()				
1b.	If 'hospital', how would you	☐ Teaching/University hospital				
	describe the type of	☐ Regional general hospital				
	hospital?	☐ Local general hospital				
		□ Other ()				
1c. And if 'hospital', what is the						
	name of the Department you work in?					
2.	Does your clinical setting	□ Yes				
	have routine access to					
	diagnostic imaging facilities					
3.	What is your primary	☐ Angiologist				
	specialty?	□ Radiologist				
		☐ Angio-surgeon				
		□ Vascular surgeon				
		☐ General surgeon				
		□ Internal medicine physician				
		☐ Phlebologist				

		□ General practitioner□ Emergency Room physician
		□ Other ()
4a.	Do you personally diagnose and treat patients with SVT and/or DVT?	□ Yes □ No
4b.	If 'no', would they be treated by someone else in your clinical setting or by someone else in a different clinical setting?	□ Same setting (specify who:) □ Different setting (specify which setting:) THANK AND CLOSE
		THAIN AND GEOSE
5a.	Including yourself, how many physicians in your setting will diagnose and treat patients with SVT?	
5b.	How many patients are currently being managed in your setting who have isolated SVT and how many have SVT with concomitant DVT?	isolated SVT SVT with concomitant DVT
6.	What proportion of these patients is treated with	% isolated SVT
7.	In a typical month, how many patients would your department diagnose with: a. Isolated SVT b. SVT with concomitant DVT	% SVT with concomitant DVT isolated SVT SVT with concomitant DVT
8a.	In what proportion of patients would you use the following procedures to diagnose SVT:	% physical examination% laboratory tests
	a. Physical examinationb. Laboratory testsc. Imaging procedures	% imaging procedures

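### Sites can be surveyed and sent a checklist naming imaging and dose while a physician's patient series is still filling, and no rule separates pre-contact from post-contact prescriptions

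*Supplement*

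**What the plan says.** Section 4 sets the standard: "It is essential that the study design and objective does not influence physician practice for treating those patients being included in the study". The safeguard drawn from it is that "the study will not begin recruitment until at least six months following availability and reimbursement of the product at the particular site". The same paragraph then allows contact inside that period ("Sites may be identified during this time period, however, recruitment will only begin after the six months have passed") and makes recruitment wait, in addition, until enough patients have accrued.

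Charts are abstracted "on the first consecutive 'n' SVT patients prescribed with fondaparinux by each physician practising at the site". Each such series opens at month 1, counted from when the product became available and reimbursed. Table 2 in Section 5.1 gives 7 patients per physician as both target and minimum, with an upper limit of 10. Section 3.3 contains no date criterion.

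Three contacts precede abstraction:

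- **Site survey (Section 4.1 and the survey script in the appendices).** Its topics include "Diagnostic criteria employed (such as physical assessment; imaging techniques, other blood tests"). The script asks about access to imaging, the proportion of patients imaged, and whether imaging is recorded.
- **Feasibility checklist (Section 4.2, Appendix 9.2).** "Physicians who could act as the lead investigator at each eligible site will be asked to review the medical charts" and tick which items are present. The items include imaging, DVT status, thrombus length, distance from the junction, and prescribed dose.
- **Briefing (Sections 4 and 4.4).** The lead investigator receives the protocol and is told the objectives before data collection.

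Sections 4.1 and 4.2 both state that the form gives no indication of the study's overall objective.

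**The concern.** A delay to recruitment protects the measured prescribing only if each patient series is already complete when the site is first approached. The plan does not require this. A physician who answers questions about imaging, or checks charts for imaging and dose, may image more often, prescribe the label dose more often, or record both better in later patients. If that physician's series is not yet full, those later patients enter the adherence estimate.

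The estimate answers an EU approval commitment about routine practice (Section 1.2) and is reported overall and per country. Any prompting would most plausibly push it upward. Section 6 does not list this limitation, and as written the analysis could neither detect the effect nor rule it out.

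**Working it through.** **1. The rules side by side**

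| Element | Rule | Source |
|---|---|---|
| Series opens | Month 1 after availability and reimbursement | Section 4 |
| Series closes | When the physician's count is reached (7 target, 10 maximum); no date | Section 4, Table 2 |
| Survey | Allowed during the six-month delay | Section 4 |
| Checklist | After the survey, before final site selection; not expressly placed inside or outside the six months | Sections 4.1, 4.2 |
| Briefing | Before data collection; the initiation call follows approvals and contracts | Sections 4, 4.4 |
| Prescription must precede contact | No such rule | Sections 3.3, 4 |

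So a post-contact prescription is eligible whenever the physician's count was incomplete at contact.

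**2. When does a site's count fill?**

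Month at which N charts exist: T(N) = 1 + N / r, where r is fondaparinux-treated SVT patients per month at the site. Section 3.1 excludes sites below 2 patients a month; I read these as SVT patients. The documents do not give the share receiving fondaparinux, so r = 2 assumes all do and r = 1 assumes half.

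| r | N = 7 (Table 2 site minimum) | N = 14 (site target) | N = 20 (site upper limit) |
|---|---|---|---|
| 2 | 1 + 7/2 = 4.5 | 1 + 14/2 = 8 | 1 + 20/2 = 11 |
| 1 | 1 + 7/1 = 8 | 1 + 14/1 = 15 | 1 + 20/1 = 21 |
| 4 | 1 + 7/4 = 2.75 | 1 + 14/4 = 4.5 | 1 + 20/4 = 6 |

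By month 6 the series has been open for 5 months, so a site at r = 2 has at most 10 charts. Reaching 14 by month 6 needs r = 14/5 = 2.8. A low-volume two-physician site contacted within the six months will therefore still be filling its series. A one-physician site, or a busier one, may already be complete.

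**3. Milestones**

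Section 7.4 puts site identification and assessment at April 2011 to December 2012, feasibility at August 2012 to March 2013, and first patient inclusion at January to July 2013. Appendix 9.5 reports feasibility already completed in Germany, Slovenia and Greece. Contact before inclusion is thus planned and partly done. Inclusion here means chart abstraction, not prescription, so these dates show that overlap is possible, not that it occurred.

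**4. What a bias could do (assumed values only)**

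The plan's power figures for 30 physicians with 7 patients each, adherence 0.8 and intra-class correlation 0.1, 0.2, 0.25 and 0.3 are 0.998, 0.974, 0.963 and 0.937. Re-simulating (20,000 runs, intercept-only GEE, logit-scale interval) gives 0.998, 0.985, 0.972 and 0.956, all within 2 points. Over the whole of Table 3, 13 of 16 cells agree within 2 points and the other three differ by 2.1 to 2.7.

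The shift in the estimate is f × d, where f is the share of charts prescribed after contact and d the rise in adherence among them. The documents give neither. With 1 of 7 exposed and d = 10 points, the shift is 1.4 points. With 2 of 7 it is 2.9. With 4 of 7 and d = 20 points it is 11.4.

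In the same simulation, at correlation 0.2 and an assumed true adherence of 0.65, the chance that the lower limit exceeds 60% is about 0.18 with no exposure. It becomes 0.26, 0.37 and 0.95 in those three cases. The illustration exposes every physician equally, which the consecutive-patient rule makes unlikely.

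**The case against.** The strongest reply is that the plan already does much of the work. Taking the first consecutive patients from month 1 favours early prescriptions and closes each series by count, so a physician who has the full count at first contact is not exposed at all. Both forms withhold the objective. The one contact that reveals it, the briefing, is planned after patients have accrued. The feasibility step reviews existing charts, up to 14 per site, and is completed by potential lead investigators rather than by every prescriber. All of this stands, and it confines the risk to incomplete series. It does not remove the risk, because the checklist names both endpoint components whether or not the aim is stated, and nothing bars the person completing it from prescribing.

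A reader might infer more than the documents support:

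- **That the index window is open-ended.** It is not; it closes on 7 to 10 patients per physician.
- **That a site at the 2-per-month floor has 29% (4/14) to 64% (9/14) of its charts exposed.** Those are shares prescribed after month 6. Month 6 is not a contact date, and the figures pair the smallest eligible site with the two-physician target.
- **That the estimate is inflated by some known number of points.** No effect size is given.
- **That the survey discloses the aim through its heading, "SVT - Physician Prescribing Study Site assessment survey".** It is a telephone script, nothing shows that the heading is read out, and the legible questions do not ask about dose.
- **That bias is confounded with country.** Launch timing varies, but no country-level launch or contact dates are given.

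**Conclusion.** The gap is real and worth closing. The plan sets a requirement of no influence on practice, permits contact before the patient series need be complete, and has no way to tell pre-contact from post-contact prescriptions. I am confident of that reading of the rules.

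The exposure is narrower. It affects physicians who have not reached 7 to 10 patients at first contact, mainly at low-volume or early-contacted sites. The accrual figures assume constant volume and, for month 8 and month 4.5, that every SVT patient receives fondaparinux. Any bias would plausibly be upward, but its size is unknown and the figures in step 4 of the check are illustrations. The documents do not support saying that the study's estimate is biased, only that it could be and that nobody would be able to tell.

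**What to change.** 1. In Section 4, require a log for each site of the dates of the survey, the feasibility questionnaire and the initiation call. Where these contacts have already taken place, recover the dates from existing records.
2. Classify each chart by whether the date fondaparinux was first prescribed, already on the CRF, precedes the site's first study contact. Use one definition of first contact in all countries, fixed before abstraction starts.
3. In Section 5.2, pre-specify the adherence estimate in pre-contact prescriptions, overall and per country, by the same GEE and reported beside the all-charts estimate. Give the number of charts in each class.
4. In Section 6, list possible post-contact prescribing as a limitation.

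Making pre-contact prescription an eligibility rule is not needed and could cost charts at the sites that have fewest. The cost of the change is a small log and one extra analysis. The pre-contact estimate will be less precise where few charts qualify. Close agreement between the two estimates would support the non-influence claim within that precision; a difference would show readers where caution is due, though calendar time could also contribute to it.
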